6.3 Exclusion criteria

Subjects who met any of the following exclusion criterion were excluded:

1. A subject didn't have an indication suitable to use the product;
2. A subject was known to be allergic to a component or ingredient of the product to be implanted, including silicone tubing, rifampicin, and clindamycin;
3. According to the comprehensive judgment of investigator, a subject had an infection of the implant site, when the shunt was implanted, such as ventriculitis, meningitis, peritonitis, and local implant skin infection;
4. A subject was simultaneously implanted another shunt system excluding Bactiseal Catheter;
5. A subject had a contraindication of the shunt operation;
6. A subject had uncorrected coagulopathy or any bleeding disorder.

7 Research Process

The research process included: Screening and enrollment of subjects, Days -30 to -1 before the operation, Day 0, the day of operation, and one-year follow-up (Days 1-365) after the operation.

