6.2 Inclusion criteria

Subjects who met all of the following inclusion criteria would be enrolled:

1. The informed consent was exempted by the Ethics Committee of a research center. Or a subject or his/her legal representative signed the informed consent form (ICF) prior to the enrollment;
2. A subject had an indication suitable to use Bactiseal Catheter;
3. A subject received hydrocephalus shunt at least one year ago.

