7.1 Screening and enrollment

7.1.1 Screening of subjects

Qualified and authorized investigators or clinical study coordinators reviewed the medical records of subjects to screen subjects eligible for this study.

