7.2 Days -30 to -1 before the operation

The following information needed to be collected and recorded:

1. Demographic information and medical history of a subject before the operation: including patient age, gender, height, weight, preoperative diagnosis; past medical history, personal history; preoperative laboratory examination results: including white blood cells, red blood cell count, neutrophilic granulocyte count, hemoglobin content, platelet count, alanine aminotransferase (ALT), aspartate aminotransferase (AST), C-reactive protein, albumin, blood glucose, APTT, PT, and INR. If there were multiple laboratory tests before the operation, the latest results should be collected.

2. Concomitant medication: Only the administration of antibiotics within seven days prior to the operation was recorded.

7.3 Operation period (Day 0, the day of operation):

The following information needed to be collected and recorded:

1. Operation: surgeon, surgical procedure, start and stop time of the operation, blood loss during the operation, intraoperative complications, intraoperative shunt, and combined treatment;

2. Record of devices used during the operation: type, No. and batch No. of the cerebral ventricular shunt catheter; type, No. and batch No. of the pressure regulating valve; and type, No. and batch No. of shunt catheters at the abdominal cavity/the lumbar cistern/ the atria.

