10.2 General considerations

The primary analysis will be descriptive in nature and will be based on information in the data collection form.

The extraction of the data from the medical records will be done by the investigators who care for the patients; in this way, the possible limitation of the study that is normally observed in other studies of review of clinical histories in which the information can be interpreted incorrectly is minimized.

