10.6 Analysis plan

All study data collected in this study will be presented in subject data listings. Statistical analyses will be performed using SAS 9.3 or later version. Other valid software might also be used as appropriate.

Data analysis will be carried out primarily using descriptive statistics. In general, mean, standard deviation, median, minimum and maximum will be calculated for continuous variables, and frequencies and percentages will be presented for categorical variables. If necessary, additional descriptive statistics may be calculated.

Analysis population

The primary analysis population for this study is the Per Protocol (PP) populations. The PP population will include all subjects who meet the inclusion/exclusion criteria

Subgroup analyses

The main subgroups that will be analyzed, in addition to the total population per protocol, will be adults and children.

Endpoint analysis

The primary endpoint of 1-year infection free survival rate will be estimated by the Kaplan-Meier method, the 95% confidence width for the survival rate will be estimated by the Peto method. The Kaplan-Meier survival curve will be presented.

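### Exclusion 3 sets no date limit on the evidence for infection at implant, so a judgment made after the outcome year could remove early infections from the primary endpoint

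*Combined protocol and SAP*

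**What the plan says.** Exclusion 3 in section 6.3 applies when "According to the comprehensive judgment of investigator, a subject had an infection of the implant site, when the shunt was implanted". The synopsis carries the same rule. Ventriculitis, meningitis, peritonitis and local skin infection at the implant are given as examples. No culture, CSF or imaging criterion is stated, and no limit is set on the date of the evidence.

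On timing, section 6.2 requires that "A subject received hydrocephalus shunt at least one year ago". On who screens and from what, section 7.1.1 says: "Qualified and authorized investigators or clinical study coordinators reviewed the medical records of subjects to screen subjects eligible for this study". Section 10.2 adds, about data collection, that "The extraction of the data from the medical records will be done by the investigators who care for the patients".

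On analysis, section 10.6 names one population: "The PP population will include all subjects who meet the inclusion/exclusion criteria". The estimator is given in the same section: "The primary endpoint of 1-year infection free survival rate will be estimated by the Kaplan-Meier method".

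Section 7.4 sorts postoperative infections into intracranial, skin and abdominal. Section 10.1 words the endpoint as freedom from CSF infection. Section 10.3 plans on a 4.3% annual infection rate and 150 subjects, of whom 100 are historical and 50 new.

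**The concern.** Excluding patients who were already infected at implant is sound. The weakness is that the rule depends on overall judgment, exercised when the outcome is already in the chart, about the condition that the study is measuring. The examples in exclusion 3 map onto the infection classes of section 7.4, and ventriculitis and meningitis also overlap the narrower CSF endpoint of section 10.1. An infection that shows itself a few days after surgery could be called an endpoint event or a pre-existing infection, and the plan gives no rule for choosing.

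The resulting error has one direction. Reading an early infection back to the day of implant removes an event and can only raise the non-infection rate. The confidence interval does not reflect this. The study has no comparator and no pass/fail criterion (section 10.4), so the descriptive rate is itself the result, and section 10.7 sends it to the regulator in support of extending the registration.

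**Working it through.** **1. The plan's own figures (section 10.3).** Inputs: N0 = 150, infection rate 4.3% (0.044 is printed in the exponent), dropout 10%, S = 0.957.

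- N(1) = 150 × exp(−(0.044 + 0.1)) = 129.9. With 0.043 it is 130.0. The plan states 130, so it reproduces either way.
- Margin = 1.96 × √(0.957² × 0.043 / 130) = 3.41%. The plan states 3.4%, which reproduces.

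**2. The sequence of decisions.**

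| Step | What the plan provides | Consequence |
|---|---|---|
| Time of judgment | At least one year after the shunt (6.2); follow-up is Days 1–365 (7) | The outcome window has closed |
| Material used | Medical records, with no restriction to preoperative ones (7.1.1) | The postoperative course is available |
| Rule | Investigator's overall judgment (6.3) | No criterion separates pre-existing from early postoperative infection |
| Analysis set | Eligible subjects only (10.6) | An excluded case leaves numerator and denominator |

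The wording of exclusion 3 fixes when the infection must have existed. It does not fix which evidence may be used to infer that.

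**3. Expected events at 4.3%.**

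- New subjects: 50 × 0.043 = 2.15, taken as 2.
- Pooled: 150 × 0.043 = 6.45, taken as 6.

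**4. Effect of moving one case.**

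- New subjects: 2/50 = 4.00% becomes 1/49 = 2.04%, a fall of 1.96 points in the infection rate.
- Pooled: 6/150 = 4.00% becomes 5/149 = 3.36%, a fall of 0.64 points.
- If the site instead enrolls another, uninfected patient to keep the numbers up: 1/50 = 2.00% (a fall of 2.00 points) and 5/150 = 3.33% (a fall of 0.67 points). The result is nearly the same.

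**5. Effect of moving two cases, both from the new subjects.**

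- New subjects: non-infection goes from 48/50 = 96.0% to 48/48 = 100%, a rise of 4.0 points.
- Pooled: 144/150 = 96.0% becomes 144/148 = 97.3%, a rise of 1.3 points.

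**6. Scale against precision.** The pooled margin is 3.4 points. The same formula for 50 subjects gives N(1) = 50 × exp(−0.144) = 43.3 and a margin of 1.96 × √(0.957² × 0.043 / 43.3) = 5.9 points. One moved case is 0.64/3.4 = 0.19 of the pooled margin and 1.96/5.9 = 0.33 of the margin for 50.

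**The case against.** The case against has several parts, and some of it stands.

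- *The criterion is already tied to the time of implant.* Calling a later infection pre-existing would breach it. This is true for an infection known to have started later. It does not help where onset is uncertain, which is where judgment is used.
- *There are safeguards.* Section 11.3.2 verifies eligibility in the source records for 100% of subjects, section 7.2 collects preoperative blood tests and recent antibiotics, and section 12.5 treats eligibility breaches as primary violations. These checks act mainly on enrolled subjects, and none supplies a decision rule for exclusion 3. The instruction in section 7.2 to take the latest preoperative laboratory results is simply collection of pre-implant evidence and is no part of the problem.
- *Excluded patients may still be recorded.* Section 7.1.2 requires records of those screened as meeting the inclusion criteria, and a patient caught by exclusion 3 could be among them. This stands: such a patient is lost from the analysis, but not clearly from the site's files. Reasons for exclusion are not explicitly required.
- *The treating clinician may not be the one who judges.* Section 10.2 concerns data extraction, and section 7.1.1 lets coordinators screen. That the treating investigator decides exclusion 3 is plausible, but it is an inference.
- *The effect is small and hypothetical.* One case is under one fifth of the pooled margin, and no pass/fail decision depends on it. This is fair, and it limits the weight of the point.

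A reader might infer that infections have been, or will be, taken out in this way. The documents give no infection counts by time from surgery and no record of exclusions, so they do not support that reading.

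**Conclusion.** The point holds as a weakness in what the rule permits. The plan allows a judgment informed by the outcome, on the endpoint condition, to decide who enters the only analysis population, and the possible error always favors a higher non-infection rate. It is a matter for improvement and does not invalidate the study.

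The size is a per-case illustration, not an estimate of bias: about 2.0 points per case in the 50 new subjects and 0.6 points in the pooled 150. It assumes the plan's 4.3% rate, event counts rounded to 2 and 6, no censoring before one year, and reclassification among new subjects only. How many infections fall early enough to be open to this reading is unknown, because the documents give no distribution of onset times.

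**What to change.** Reword exclusion 3, in section 6.3 and the synopsis, so that it applies only when infection at implant is documented by samples, imaging or notes dated on or before the day of operation. For samples, use the date of collection and not the date of the report. In the study report, give the number of patients excluded under this criterion at each center, with the type and date of the supporting evidence.

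The cost is a wording change, an entry in the screening log and one short table. The downside is that a few true pre-existing infections, proven only by later samples, would be counted as events.

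Asking for eligibility to be settled before postoperative notes are opened should not be presented as blinding, because clinicians who treated the patient may already know the course.

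A sensitivity estimate that counts exclusion-3 patients with postoperative infection as events is optional. It needs outcome data on people who were not enrolled, so it should be limited to centers with a consent waiver or to patients who consented (section 7.1.2). It would also count the persistence of genuine pre-implant infection as a new event, so it should be labeled a worst-case bound.

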7.1 Screening and enrollment

7.1.1 Screening of subjects

Qualified and authorized investigators or clinical study coordinators reviewed the medical records of subjects to screen subjects eligible for this study.

7.1.2 Informed consent

As this was a retrospective study, it would apply for the exemption of informed consent from the Ethics Committee of a center. For the centers which did not exempt informed consent, the informed consent process would be completed prior to the start of data collection, either by telephone or by any means approved by the Ethics Committees. If informed consent was not obtained from a subject of a center which did not exempt informed consent, the subject could not participate in this study.

Research centers should maintain records of subjects who were screened to meet the general inclusion criteria and signed the ICF (in terms of a research center that did not waive informed consent).

7.1.3 Enrollment of subjects

If a subject met all the inclusion criteria and did not meet any exclusion criterion, he/she could be included in the retrospective analysis cohort. Subjects could be considered as enrolled in this study only if they met the following requirements:

- 1) A subject met all the inclusion criteria and did not meet any exclusion criterion; and
- 2) The ICF was signed (in terms of a research center that did not waive informed consent).

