11.3.3 Case Record Form (CRF)	19
11.3.4 Archive and data retention.....	19
11.3.5 Audit and inspection.....	19
12 Ethical and Regulatory Requirements	20
12.1 Ethics Committee	20
12.2 Informed consent	20
12.3 Subject confidentiality.....	21
12.4 Revision of the study proposal	21
12.5 Proposal deviation.....	21
13 Publication Policies.....	21
14 Devices.....	22
14.1 Count of research-related devices	22
14.2 Return of research-related devices	22

Proposal No.: C-BSEAL-001

Date of proposal: V1.0/2019-11-18

14.3 Complaint about devices	22
14.3.1 Complaint about devices	22
References	23
Table 1: Product Specifications and Models.....	6

Summary of the Proposal

Research Topic:	A Multi-center, Retrospective Registry Study on the Safety of Bactiseal Catheterization
Research Purpose:	This study aimed to continue to evaluate safety information from subjects implanted with a catheter (trade name: Bactiseal) produced by Codman & Shurtleff, Inc. of the United States. Device safety would be assessed based on all the adverse events that occurred within one year after the subjects implanted the catheter.
No. of Subjects:	50
No. of Research Centers:	3 research centers
Research Design:	
This study was designed to be single arm, multi-center, and retrospective.
 
A total of 50 patients would be retrospectively enrolled. Information would be collected on adverse events of subjects enrolled within one year after the implantation of the Bactiseal Catheter from August 07, 2018 to January 31, 2021.
 
The following information would be collected from subjects' medical records or hospitals' databases (if any):
 
 1. General condition of the subjects 2. Intraoperative condition and catheter implantation 3. Information on the shunt product 4. Adverse events of subjects within one year after the operation and classification of the adverse events 5. Relevant examinations in case of postoperative infection 6. Other adverse event-related information (except anticipated adverse events)
Research Duration:	2020-

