3.2 Purpose

This study aimed to collect safety information from subjects implanted with a catheter (trade name: Bactiseal) produced by Codman & Shurtleff, Inc. of the United States. Device safety would be assessed based on all the adverse events that occurred within one year after the subjects were implanted with the catheter.

4. Research Design

This study was designed to be single arm, multi-center, and retrospective.

This is continued access study to enroll additional 50 new subjects, with total combined 150 subjects. The historical study is DPS-201501.

It would collect information on adverse events of subjects enrolled within one year after the implantation of Bactiseal Catheter from August 07, 2018 to August 31, 2019, through case review or hospital database (if any).

The following information would be collected from subjects' medical records:

1. General condition of the subjects
2. Intraoperative condition and catheter implantation
3. Information on the shunt product
4. Adverse events of subjects within one year after the operation and classification of the adverse events
5. Relevant examinations in case of postoperative infection
6. Other adverse event-related information (except anticipated adverse events)

Information on adverse events would be collected. And the safety of clinical application of the product would be assessed.

5. Endpoint

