6.1 Selection of subjects

Subjects who received a hydrocephalus shunt operation between August 07, 2018 to August 31, 2019 and met the inclusion criteria were enrolled. As this was a retrospective study, it would apply for the exemption of informed consent from the Ethics Committee of a center. For the centers which did not exempt informed consent, the informed consent process would be completed prior to the start of data collection, either by telephone or by anyway approved by the Ethics Committees.

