11.4 Data Collection and Management Responsibilities

Data collection is the responsibility of the clinical trial staff at the site under the supervision of the site Investigator. The Investigator is responsible for ensuring the accuracy, completeness, legibility, and timeliness of the data reported.

The recruitment of the study centers and the extraction of data from patients' medical records will be closely monitored to reach the proposed sample sizes. The study investigators will be asked to extract the data from the medical records of all patients implanted with Hakim programmable shunt system for the study in their respective centers. Integra Clinical Operations will follow up with the centers during the data collection process when appropriate to ensure a rapid completion of the data collection process.

Hardcopies of the study visit CRFs will be provided for use to collect data for each subject enrolled in the study. Data recorded in the CRFs derived from any source documents should be consistent with the data recorded on those source documents.

Clinical data (including AEs), concomitant medications, and expected adverse reactions data) and clinical laboratory data will be entered into Microsoft Access Database by Sponsor by double data entry. The data will be reviewed and validated. Queries for any missing, inconsistent or illogical data points will be forwarded to the research center for resolution. After all data queries are resolved, the data will be transferred to a biostatistician for analysis.

12 Ethical and Regulatory Requirements

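### Infection status is already in the chart at screening, and no rule says which 50 Bactiseal patients to enrol if more than 50 are eligible

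*Combined protocol and SAP*

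**What the plan says.** **Timing.** Inclusion criterion 3 in section 6.2 reads "A subject received hydrocephalus shunt at least one year ago". The one-year follow-up period has therefore run out before a patient can be screened.

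**Who screens and who extracts.** Under section 7.1.1, "investigators or clinical study coordinators reviewed the medical records of subjects to screen subjects eligible for this study". Section 10.2 gives data extraction to the investigators who look after the patients. Neither section separates selection from knowledge of the outcome.

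**How many.** The Summary states: "A total of 50 patients would be retrospectively enrolled". Section 4 says: "This is continued access study to enroll additional 50 new subjects, with total combined 150 subjects". Three centres take part. No per-centre number is given.

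**Which patients.** Three places bear on this:

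- Section 6.1: "Subjects who received a hydrocephalus shunt operation between August 07, 2018 to August 31, 2019 and met the inclusion criteria were enrolled".
- Section 7.1.3: a patient who meets every inclusion criterion and no exclusion criterion is one of whom the plan says "he/she could be included in the retrospective analysis cohort". The same section then lists the conditions for counting as enrolled: eligibility, and consent where it is not waived.
- Section 11.4: investigators are to "extract the data from the medical records of all patients implanted with Hakim programmable shunt system for the study in their respective centers".

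**The window.** Section 6.1 ends the operation window at August 31, 2019, and section 4 ends its range on the same date. The parallel sentence in the Summary ends it at January 31, 2021.

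**The concern.** When the outcome is known before a patient is chosen, the choice itself can depend on the outcome. Prospective enrolment excludes this by its order in time. A retrospective cohort needs a written rule instead: everyone eligible, or a fixed sequence. The plan fixes a target of 50 but has no rule for reaching it if the eligible pool is larger.

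Intent is not required. Preferring charts that are complete, or easy to close, would have the same effect if infected patients tend to have longer or more scattered records.

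The one-year infection-free rate is the primary endpoint (10.1, 10.6), and the report supports extension of the product registration (10.7). Only a handful of infections are expected, so a few patients left out would move the estimate. The Kaplan-Meier analysis cannot detect or repair this, and its confidence interval measures sampling error only.

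**Working it through.** **1. The plan's own figures (section 10.3).** Inputs: N0 = 150 (100 historical, 50 new), one-year infection rate 4.3%, dropout 10%, S(1) = 95.7%.

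- N(1) = 150 × exp(−(0.044 + 0.1)) = 129.9. With 0.043 in place of the printed 0.044 it is 130.0. Both round to the stated 130.
- Margin = 1.96 × √(0.957² × 0.043 / 130) = 0.0341, the stated 3.4%.

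This margin belongs to the pooled 150. For the new 50 alone, N(1) = 50 × exp(−0.143) = 43.3, and the margin is 1.96 × √(0.957² × 0.043 / 43.3) = 5.9 points.

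**2. Expected infections without selection.** 50 × 0.043 = 2.15 among the new subjects and 150 × 0.043 = 6.45 in the pool. Because the target is fixed at 50, an infected patient passed over is replaced by an uninfected one. Each such replacement lowers the new-cohort rate by 1/50 = 2.0 points and the pooled rate by 1/150 = 0.67 points.

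**3. Partial selection.** Let w be the chance that an infected patient is chosen, relative to an uninfected one. The documents give no value, so w is an assumption and a range is shown. With a large eligible pool:

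- new-cohort rate = 0.043w / (0.043w + 0.957)
- pooled rate = (100 × 0.043 + 50 × new-cohort rate) / 150

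The historical 100 are taken to run at 4.3%. Rates are crude proportions.

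| w | New 50 | Pooled 150 | Bias in pooled rate |
|---|---|---|---|
| 1 | 4.3% | 4.3% | 0 |
| 0.75 | 3.3% | 4.0% | 0.3 points |
| 0.5 | 2.2% | 3.6% | 0.7 points |
| 0.25 | 1.1% | 3.2% | 1.1 points |
| 0 | 0% | 2.9% | 1.4 points |

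The last row is the limit: 4.3% × 50/150 = 1.43 points, or 1.43/3.41 = 42% of the margin. At the literature rate of 3.2%, the limit is 3.2% × 50/150 = 1.07 points. With w = 0.5 at that rate, the new cohort is at 0.016/(0.016 + 0.968) = 1.6% and the pool at (3.2 + 0.81)/150 = 2.7%, a bias of about 0.5 points.

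**4. How many eligible patients make the limit reachable.** Let M be the number eligible (not given) and X ~ Binomial(M, 0.043) the number infected among them. If 50 are chosen avoiding infected patients where possible, the expected number infected among those chosen is E[max(0, X − (M − 50))].

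| M | Expected infections among the 50 | Chance that 50 uninfected patients are available | Pooled rate |
|---|---|---|---|
| 50 | 2.15 | 11% | 4.3% |
| 51 | 1.30 | 35% | 3.7% |
| 52 | 0.68 | 61% | 3.3% |
| 55 | 0.04 | 97% | 2.9% |
| 60 | 0.00 | 100% | 2.9% |

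With M = 50 there is no choice and no bias. About five surplus patients are enough to reach the limit.

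**5. Whether another section closes the gap.**

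- Section 10.6 puts all subjects who meet the criteria into the per-protocol population. That governs the analysis of collected subjects, not who is collected.
- Section 11.3.2 requires verification against the CRF entries of 100% of subjects for criteria and endpoints. Patients for whom no CRF was opened are not seen.
- Section 7.1.2 requires records of those who met the general inclusion criteria and signed consent. It asks for no list of eligible patients left out.

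**The case against.** The strongest reply rests on section 6.1. Its wording is unconditional, and its most natural reading is an eligible-patient cohort. Section 11.4 does ask for all patients, and its Hakim wording looks like a product-name error; once corrected, it would supply most of the missing rule. The study is also descriptive, with no pass/fail criterion (10.2, 10.4).

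Much of this stands. A reader might take the verb in section 7.1.3 as leaving inclusion to the investigator's discretion. The documents do not support that: the protocol uses the same conditional style throughout, and the sentence sets conditions of eligibility. The gap is silence, not a permission. For the same reason it goes too far to say that any 50 eligible patients plainly satisfy the plan, since section 6.1 points the other way.

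The reply does not close the gap. Section 6.1 does not say that every eligible patient is taken, and an all-eligible reading cannot be squared with a fixed 50 if more are eligible. The end of the window also differs between the Summary and the body. Section 11.4 as written directs extraction to recipients of another product. A descriptive aim does not help either, because the infection-free rate is what the study is there to describe.

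**Conclusion.** The concern holds as a gap in the selection rule, conditional on more than 50 patients being eligible. In that case the plan as written permits selection with knowledge of infection. With 50 or fewer eligible, no choice arises. The documents do not give the number.

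At 4.3%, the bias in the pooled rate is about 0.7 points if infected new patients are half as likely to be chosen, and at most about 1.4 points if none is enrolled, against a 3.4-point margin that does not include it. These figures assume crude proportions, unselected historical subjects at 4.3%, and the stated values of w and M. They show what is possible and do not estimate what happened.

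Two stronger readings should be resisted. A reader might set the fall of about 2 points in the new cohort (4.3% to 2.2%) against the 3.4-point margin. The two are on different scales: 3.4 points belongs to the pooled 150, where the same scenario gives 0.7 points, and the new 50 alone have a margin of 5.9 points. A reader might also infer that infected patients were in fact passed over. Nothing in the documents shows that.

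**What to change.** - **Sections 6.1 and 7.1.3:** state that all eligible Bactiseal recipients operated on in the window are enrolled. If more than 50 are eligible, state that they are enrolled consecutively by operation date from the start of the window until 50 is reached across the three centres. If per-centre numbers are preferred, they must be added and fixed before screening, since the plan has none. With such a rule the screener need not be blinded to postoperative records, which would be hard to guarantee when treating investigators handle the charts.
- **Section 11.4:** replace the Hakim system with Bactiseal and state the same rule.
- **Window:** reconcile the end date in the Summary with that in sections 4 and 6.1, so that one source population is defined.
- **Log:** at each centre, record every eligible patient, whether enrolled, and the reason if not (including consent not obtained where it is not waived). Report the counts.

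The cost is a few sentences, a screening log and a count in the report. No patients are added, and N0 = 150, N(1) = 130 and the 3.4% margin are unchanged.
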